Anxiety and Depressive symptoms: The Hopkins Symptom Checklist-25 (HSCL-25)² will be used to measure anxiety and depressive symptoms experienced over the past month at baseline, post-intervention, and three-month post-intervention. It is composed of a 10-item subscale for anxiety and a 15-item subscale for depression, with each item scored on a Likert scale from 1 (not at all) to 4 (extremely).

Secondary outcome

Physiological stress: Cortisol hair-test (average hormone levels over the past three months) will be used as a biomarker to measure physiological stress. Neuroendocrine indicators, such as cortisol, are effective stress biomarkers because they are the first to respond to a given stressor and coordinate the physiological response of other bio-physiological systems.

Interventions and Duration

Study Arms:

Experimental: Problem Management Plus for Immigrants (PMP-I) at family settings

Active Comparator: Talk program with Community Support Service Pamphlet (CSS)

Assessment:

Baseline, Post-Intervention, and 3-month Post-Intervention

Intervention:

PMP-I is a 5-week, peer-led, culturally tailored psychoeducation, behavioral activation, and problem-solving (90 minutes), breathing and yoga intervention (90 minutes) in a family setting. PMP-I will use a structured approach, including once a week, face-to-face sessions, breathing, yoga practice, homework that includes recording activities, rebuilding individual skills, or learning new skills to reduce stress.

- 1. Managing Stress:** Breathing and yoga practices, stress-management sessions, and behavioral activation exercises to strengthen positive coping strategies.
- 2. Managing Problems:** Practice exercises to identify the problems, develop solutions, and plan a strategy to carry out those solutions.
- 3. Behavior Activation:** Communication skill sessions and practice exercises to identify and carry out pleasant tasks.
- 4. Strengthening Social Support:** Social skills session and practice exercise to identify social support.
- 5. Staying Well:** Make a plan that helps to create a supportive family environment.

Sample Size and Population

This study will be conducted among 226 Bhutanese adults settled in Massachusetts.

STUDY TEAM ROSTER

Principal Investigator: [name]., MPH, MPHC, CGM
Assistant Professor, College of Nursing, [name], University Massachusetts Amherst, MA, 01003
Email: [contact]
[contact]

Co-Investigator: [name].

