5 STUDY INTERVENTIONS

5.1 Interventions, Administration, and Duration

Intervention group: Each participant's involvement will be 5-sessions of the PMP-I program of 180 minutes each for a total of 900 minutes. We will request intervention group participants to complete five sessions of PMP-I intervention. Each session is about 180 minutes. Our proposed family-based mental health intervention is a 5-week, culturally tailored stress management, behavioral activation, problem-solving (90 minutes), and mind-body exercises, including yoga and breathing exercises (90 minutes) at a family level delivered by trained community interventionists at their family settings.

Control group: We also plan to implement five talk programs about community support services to control group participants. Each participant's involvement will be 5-sessions of a talk program of 60 minutes each for a total of 300 minutes.

Post-Intervention for Control group: Each participant's involvement will be 2-sessions of mental health intervention of 120 minutes each for a total of 240 minutes.

Training for Community Interventionists: We will train community members to deliver the intervention in family settings. [name] will provide 12 full-day training to the community interventionists in collaboration with PI and [name] [name] following the World Health Organization PM+ training manual. We will provide a PMP-I program manual describing the procedure of delivering each intervention component to community interventionists. They will use the intervention manual to provide PMP-I to community members at family settings under field supervisors and PI's supervision. (Please see attached the PMP-I intervention manual for the details)

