9 STATISTICAL CONSIDERATIONS

9.1 Sample Size and Randomization

The pilot project aims to estimate the magnitude of the difference between the preventive intervention and the education control on the primary outcomes of interest (stress, anxiety, depressive symptoms) to inform the design of a large-scale intervention. A study comparing PMP to a treatment-as-usual control in Pakistan⁶¹ found a mean difference of about 7 points with a standard deviation of 8.5 on a measure of anxiety and depression for effect size ($ES=.86$). We do not expect our ES to be as large as what was observed in the Pakistani study⁶¹ given that we are doing a prevention trial and not an intervention study in a distressed population so that this study will provide an estimate of the ES of PMP as a preventive intervention.

We conducted a power analysis to detect an ES as small as $ES=.30$ with $\alpha = .05$ and power of $.80$. We may find a larger effect in our pilot, but our understanding is that power estimates should be based on the smallest effect that we want to detect rather than the size of the effect that we expect.⁶² We expect that families will average approximately 2-4 adult persons based on our pilot data, and conducted our power analysis to account for the correlation among family members. Analyses were conducted using Optimal Design,⁶³ which is power analysis software created for cluster randomized trials such as the present study. Accounting for the intra-correlation among family members of $.10$ and $\alpha = .05$, we would have 80% power to detect a standardized difference of $ES=.30$ between two treatment groups of 116 families (58 per treatment arm) with an equal probability of being randomized to each of our two intervention arms.

As noted above, we do not expect our ES to be as large as in the Pakistani study, but a sample of that size should be sufficient to provide the estimates of the differences between the conditions (with standard deviation in our sample) and the correlations between the targets specified by theory and our primary outcome of interest to inform the design of a larger-scale controlled trial. The other goal for the project is to determine whether the intervention affects the target mechanisms specified by theory to mediate or moderate the intervention's impact on the outcomes. Those estimates we will get from the correlation between our respective targets (coping and self-efficacy) and the primary outcomes.

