The primary analyses will test whether participants' outcomes in the PMP-I arm differ from those in the control arm. Multilevel modeling will compare outcomes of each treatment arm while accounting for the clustering of participants within families. Continuous outcomes will be analyzed using hierarchical linear modeling, and dichotomous outcomes will be analyzed using multilevel generalized linear models with a Bernoulli distribution appropriate to nonlinear binary outcomes.⁶⁴ We expect approximately 2-4 members for each of the 58 families in each treatment arm, and the correlation among family members' responses will be accounted for in the model. Hierarchical or multilevel modeling is suited to these data as it accounts for the clustering of members within families and unbalanced designs (i.e., different family sizes).⁶⁴ This will be an intention-to-treat type of analysis, as multilevel modeling allows retention of all participants irrespective of the number of sessions attended (multilevel modeling uses maximum likelihood estimation, one of the recommended ways of handling missing data). The analysis will estimate endpoint outcomes based on repeated measures (Level 1) within individuals (Level 2) within families (Level 3). This three-level model is represented by the following equations:

Level 1: $Outcome_{ijk} = \pi_{0jk} + \pi_{1jk} * Time_{ijk} + e_{ijk}$; Level 2: $\pi_{0jk} = \beta_{00k} + r_{0jk}$; $\pi_{1jk} = \beta_{10k} + r_{1jk}$
 Level 3: $\beta_{00k} = \gamma_{000} + \gamma_{001} * PMP-I_k + u_{00k}$; $\beta_{10k} = \gamma_{100} + \gamma_{101} * PMP-I_k + u_{10k}$

[figure not shown]

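### The Aim 2b model has no interventionist term, so if families share lay deliverers in the PMP-I arm and deliverers differ, the standard error of the key contrast may be too small

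*Combined protocol and SAP*

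**What the plan says.** Section 9.2 (Data Analyses, Aim 2b) describes the primary analysis: "Multilevel modeling will compare outcomes of each treatment arm while accounting for the clustering of participants within families". The equations place repeated measures within individuals within families. The treatment coefficient gamma_001 sits at the family level, and the only random effects there are those of the family. The section calls gamma_001 the key test, expects it to be significant, and says that the effect-size estimates are to inform a full-scale trial. The mediation equations for Aim 2c also carry only a family random effect.

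Section 9.1 bases the sample size on "116 families (58 per treatment arm) with an equal probability of being randomized", a family ICC of .10, a standardised effect of .30, alpha .05 and power .80. On family size it says: "We expect that families will average approximately 2-4 adult persons based on our pilot data". Correlation among family members is the only clustering that it allows for.

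Section 5.1 says who delivers PMP-I: "We will train community members to deliver the intervention in family settings". They are lay people with high-school education. Each receives ten classroom days, two days of supervision training, 20 hours of breathing and yoga training (4 + 16), field training over five sessions and a readiness evaluation. The documents do not say how many interventionists there are, how families are allotted to them, or who gives the control talks.

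**The concern.** With that amount of training per person, 58 families are very unlikely to have 58 interventionists. If one person delivers to several families, whatever that person does better or worse is shared by all of them. A family random effect cannot absorb this. A deviation common to one interventionist's families averages out over the number of interventionists, not over 58 families. If the effect exists only in the PMP-I arm, or differs between arms, it passes straight into gamma_001.

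The protocol itself treats delivery as something that can vary: section 5.2 has supervisors score manual adherence, content delivered and use of time. None of this is linked to the outcome model.

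Two things are at stake. The interval and test for the key contrast may be too optimistic. And a full trial with the same lay delivery would need some idea of this variance component, which cannot be estimated later if the family-to-interventionist link is not kept.

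**Working it through.** **Inputs from section 9.1:** 58 families per arm; family ICC .10; effect .30; alpha .05 (two-sided taken, as sidedness is not stated); m = 2 to 4 adults per family.

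**Assumptions, because the documents give no figure:** C = 4 to 12 interventionists with equal loads; interventionist ICC r = .01, .02 or .05; deliverer effects in the PMP-I arm only; equal family sizes; total variance 1, with r taken out of the family share of .10. The endpoint contrast is treated as a comparison of family means.

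**Step 1. Reproduce the stated 80%.** The variance of a family mean is T = .10 + .90/m, and SE = √(2T/58).
- m = 4: T = .325, SE = √(.650/58) = .1059. Power = Φ(.30/.1059 − 1.96) = 80.9% (80.2% with t on 114 df). The stated figure reproduces.
- m = 3: T = .400, SE = .1174, power 72.4%.
- m = 2: T = .550, SE = .1377, power 58.6%. The synopsis total of 226 adults is 226/116 = 1.95 per family, so m = 2 is also a relevant case.

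**Step 2. True variance with shared interventionists.**
PMP-I arm mean: Vp = r/C + (T − r)/58. Contrast: V = Vp + T/58.

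**Step 3. What the family-only analysis estimates.** The expected sample variance of PMP-I family means is E = (58/57)(T − Vp), so the estimated SE² is (T + E)/58. The ratio is R = √[V / ((T + E)/58)], and the type I error is P(|t₁₁₄| > 1.981/R).

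*Example, m = 2, C = 6, r = .02:*
- Vp = .02/6 + .53/58 = .01247
- V = .01247 + .55/58 = .02195, true SE .1482
- E = (58/57)(.55 − .01247) = .5470
- estimated SE² = (.55 + .5470)/58 = .01891, SE .1375
- R = .1482/.1375 = 1.08; type I error .069.

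*Upper extreme, m = 4, C = 4, r = .05:*
- Vp = .0125 + .275/58 = .01724
- V = .01724 + .325/58 = .02284, true SE .1511
- E = (58/57)(.325 − .01724) = .3132
- estimated SE² = (.325 + .3132)/58 = .01100, SE .1049
- R = 1.44; type I error .172. Against the nominal SE of .1059 instead, the ratio is 1.43 and the type I error .170.

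**Step 4. Full range** (R / type I error):

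| m | C | r = .01 | r = .02 | r = .05 |
|---|---|---|---|---|
| 2 | 4 | 1.06 / .064 | 1.12 / .079 | 1.28 / .124 |
| 2 | 6 | 1.04 / .059 | 1.08 / .069 | 1.18 / .097 |
| 2 | 8 | 1.03 / .057 | 1.06 / .063 | 1.14 / .084 |
| 2 | 12 | 1.02 / .054 | 1.03 / .058 | 1.09 / .071 |
| 4 | 4 | 1.10 / .075 | 1.19 / .100 | 1.44 / .172 |
| 4 | 6 | 1.07 / .066 | 1.13 / .082 | 1.30 / .130 |
| 4 | 8 | 1.05 / .061 | 1.09 / .073 | 1.22 / .108 |
| 4 | 12 | 1.03 / .057 | 1.06 / .064 | 1.14 / .085 |

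A ratio of 1.28 means that the reported SE is 1 − 1/1.28 = 22% too small. With 2 adults the understatement runs from 2% to 22%. At m = 4, power at the true SE falls from 81% to between 79% and 51% (normal approximation).

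**Step 5. Simulation checks** (8,000 runs per setting). At m = 4 and C = 6, type I error was .085 for r = .02 and .132 for r = .05, close to the table. At r = 0 (C = 6, m = 3) it was .046, so there was no inflation.

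**The case against.** The strongest reply is that the inflation is conditional and that the documents leave every condition open. A reader might infer that the standard error is simply too small, or that PMP-I rests on a handful of interventionists. The documents support neither as fact. They give no count, allotment or ICC. The study-team pages are only partly available, and the PMP-I manual and monitoring tools are attachments outside this text, so staffing detail may sit there.

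The control arm matters too. If the same people gave the control talks, a deliverer effect common to both arms would largely cancel. Simulation with 2 adults per family, deliverers crossed with arm and no deliverer-by-arm interaction gave type I errors of .045 (6 deliverers, ICC .02), .040 (6, ICC .05) and .042 (4, ICC .05). That stands as a real limit on the claim.

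A reader might also infer that the pilot will yield no ICC for the full trial. That is wrong: the planned model gives the family ICC. Only the interventionist ICC is unplanned, and it would be imprecise. With 6 interventionists, 3 adults per family and a true value of .02, 95% of estimates lay between about −.03 and .11, and 34% were zero or below.

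Finally, manualised delivery, common training and supervision should hold down differences between interventionists, and the helper-specific forms in section 5.2 may already identify them. This lowers the likely ICC but does not replace a model term.

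**Conclusion.** The point stands in conditional form. Sections 9.1 and 9.2 allow for family clustering only, and section 5.1 makes shared interventionists in the PMP-I arm very probable. If their ICC exceeds zero and their effect does not cancel against the control arm, the test of gamma_001 is anti-conservative.

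The size cannot be fixed from the documents. Over the assumed range it goes from negligible (ratio 1.02, type I error .054) to serious (1.44, .172). The high end needs both an ICC of .05 and few interventionists, and nothing in the documents supports that ICC in particular. At ICC .01 to .02 with 6 to 12 interventionists and 2 adults per family, type I error is only .054 to .069. This is an inexpensive improvement to a pilot whose purpose is to plan a larger trial, not a reason to replace the primary model or change the sample size.

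**What to change.** - State the number of interventionists, how families are allotted to them, and who gives the control talks.
- Record the deliverer ID for every PMP-I family on the existing session checklist. Do the same in the control arm if its talks have shared deliverers.
- Keep the Aim 2b model as primary. Add a prespecified sensitivity analysis with a random intercept for interventionist in the PMP-I arm (partially nested), or with deliverers crossed with arm if the same people serve both. Use Kenward-Roger degrees of freedom.
- Report the number of interventionists and the interventionist ICC with its interval, labelled as an imprecise planning input, beside the family ICC.

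The cost is one ID field and one more model. The sensitivity interval will be wider, and with few interventionists the variance component will be poorly estimated and may come out at zero. A zero estimate should not be read as evidence that interventionists do not differ.

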Where the outcome is measured at each repeated measure *i* for each individual *j* within each family *k*. Time is centered at the endpoint, so that β_{00k} estimates the value of the outcome for each family at the end of the study, informed by all data points available for that family. If an endpoint observation is missing due to drop out, the advantage of multilevel modeling is that it utilizes maximum likelihood estimation, which estimates the expected outcome for that cluster using information from prior assessments as well as the expected value from the entire model. The key test of difference in the outcome between the treatment groups is represented by γ_{001} (in bold); this is a test of difference in outcome at endpoint between families randomized to PMP versus not. We expect this test of difference to be statistically significant based on our power analysis for the difference in outcome *level* at the endpoint. Note that this model will also test group differences in *change* in each outcome (γ_{101}). While our pilot is not powered for the significance of effects of change over time, we will be able to obtain estimates of ES for change for use in future larger-scale trials and analyses.

The ultimate goal of our analyses is to estimate the ES for this prevention trial for each outcome, to inform our planning of a full-scale trial. As noted earlier, we have powered this pilot prevention trial with a conservative estimate of effect size based on a similar study in a clinical population, but no known studies have characterized the precise effect size of PMP as a preventive intervention; a goal of our pilot is to estimate the expected effect on the population of interest (i.e. an at-risk vs clinical population). All analyses will be performed using SAS, version 9 (SAS Institute Inc, Cary, NC).

Aim 2c Mediating effects: Separate models will be created to evaluate the relationships between mediators (targets) and outcomes and to explore mediators (e.g. coping) of intervention-outcome relation.

In this aim, we aim to test the potential *mediators* of the treatment-outcome association by conducting mediational analyses in a multilevel regression framework.⁶⁵ Following current

[figure not shown]
Figure 1 Mediational Analysis Framework

recommended best practices in mediational analysis, we will conduct these analyses using recommended practices for mediation with a multilevel framework.⁶⁶⁻⁶⁸

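### For PSS and HSCL-25 scores the key test is the gap between two fitted straight lines at Day 132; it equals the 3-month arm difference only if that difference is linear in Time, and the spacing of Time is not stated

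*Combined protocol and SAP*

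**What the plan says.** Section 9.2, Aim 2b, sets out a three-level model of repeated measures within persons within families. Level 1 has an intercept and one slope on Time. Arm enters the intercept (gamma_001) and the slope (gamma_101). "Time is centered at the endpoint", and gamma_001 is the key test: "this is a test of difference in outcome at endpoint between families randomized to PMP versus not". On power, the section adds "We expect this test of difference to be statistically significant based on our power analysis for the difference in outcome", meaning its level at the endpoint.

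On purpose, the same section states "The ultimate goal of our analyses is to estimate the ES for this prevention trial for each outcome". For gamma_101 it says "we will be able to obtain estimates of ES for change for use in future larger-scale trials and analyses".

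Section 3 gives three time points for PSS and HSCL-25 and two for hair cortisol. Sections 6.1, 6.2.3 and 6.2.4 place the three at Days 0, 42 and 132, with the last session at Day 35. The plan does not say whether Time is elapsed time or visit number. It has no visit factor, no curved or piecewise term, no linearity check and no alternative time model.

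**The concern.** Each arm has three visit means and two fitted parameters, so the model forces each arm's means onto a line. The coefficient described as the endpoint difference therefore also draws on the Day 0 and Day 42 differences.

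A linear arm difference would have to keep growing at the same rate for the 97 days between the last session (Day 35) and Day 132. A difference that appears by Day 42 and then holds or fades is at least as plausible. Section 5.1 also gives controls two mental health sessions after the intervention period, without saying whether these fall before Day 132. If they do, the gap could narrow. The documents give no trajectory data, so these are possibilities only.

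At stake is the effect size, the pilot's main product. The bias does not shrink with sample size, its sign depends on an unknown trajectory, and its size depends on a coding choice left open.

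**Working it through.** **The plan's own figure.** Section 9.1 states 80% power for ES .30 with 116 families and ICC .10. With lambda = 116 x .30² / (4 x (.10 + .90/m)), a noncentral t on 114 df and a two-sided 5% test (sidedness is not stated), power is .802 at m = 4 adults per family, .717 at 3 and .579 at 2. The figure reproduces at the top of the stated range of 2 to 4. It concerns a single endpoint difference, and nothing below depends on it.

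**Weights.** For a line with its intercept at the last visit, each visit's weight is 1/3 + (t_last - mean t)(t_i - mean t) / sum of (t - mean t)².

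- Elapsed days: the mean is 58, the deviations are -58, -16 and 74, and the sum of squares is 9096. The weights are .3333 - .4719 = -.139; .3333 - .1302 = .203; .3333 + .6020 = .935.
- Visit index 0/1/2: the deviations are -1, 0 and 1, and the sum of squares is 2. The weights are -.167, .333 and .833.
- Days or weeks give the same weights. Spacing matters; unit does not.
- Generalized least squares with the plan's random intercepts and slopes gives the same weights when data are complete.
- With two visits (hair cortisol) the weights are 0 and 1, so gamma_001 is already the 3-month difference.

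**Effect on the estimate.** Assumed trajectories, effect .30 SD, no baseline difference, complete data:

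| Arm difference at Days 0, 42, 132 | Day 132 truth | gamma_001, days | gamma_001, index |
|---|---|---|---|
| Held: 0, .30, .30 | .30 | .34 | .35 |
| Half faded: 0, .30, .15 | .15 | .20 | .23 |
| Gone: 0, .30, 0 | 0 | .06 | .10 |
| Late: 0, 0, .30 | .30 | .28 | .25 |

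For example, the held case in days is .30 x (.203 + .935) = .34.

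The change effect (gamma_101 scaled to the whole period) has weights -.842, -.232 and 1.074 in days. That gives .25 against .30 (held), .09 against .15 (half), -.07 against 0 (gone) and .32 against .30 (late). With index coding the weights are -1, 0 and 1, and it is exact.

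**Against the standard error.** SE = sqrt(4/N x (1 + (m - 1) x .10) x f), with f = (1 - r) x (sum of squared weights) + r. The sum of squared weights is .935 (days) or .833 (index). N runs from 226 (protocol synopsis) to 464 (116 families of 4), m = N/116, and r, the correlation between visits, is assumed to be .3 to .7.

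- At N = 226 the SE is .136 to .138 (days) or .131 to .136 (index). At N = 464 it is .103 to .105 or .099 to .103.
- Absolute bias over the four patterns is 0.14 to 1.01 SE.
- In the gone case a nominal 5% test rejects 7% to 9% of the time (days) or 11% to 17% (index).

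**Dropout.** The plan gives no rate. If 10% to 30% of both arms miss Day 132 at random (assumption), gamma_001 over both codings is .35 to .37 held, .21 to .26 half faded, .07 to .15 gone and .23 to .28 late.

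**The case against.** The plan is open about borrowing from earlier visits and gives dropout as the reason. A line is economical, and the bias is smaller than the pilot's standard error in nearly every case examined. At 226 adults the held pattern costs only 1% to 4% in root mean squared error relative to a visit-factor estimate, and for a late effect in days coding the line is marginally better. The 17% rejection rate needs the largest families, index coding and a fully vanished effect together. All of that stands and limits the severity. The dropout argument does not rescue linearity: a likelihood model with categorical visits also uses earlier data from people who leave.

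A reader might infer more than the documents support:

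- *The test is invalid.* With complete data, a time course common to both arms cancels, and the 5% level holds when there is no effect at any visit.
- *The effect will be overstated.* The sign depends on the trajectory; a late effect is understated.
- *The next trial will be mis-sized.* Section 9.1 sizes on the smallest effect worth detecting, not on a pilot estimate.
- *Every outcome is affected.* Hair cortisol is not. For binary outcomes the plan says "dichotomous outcomes will be analyzed using multilevel generalized linear models with a Bernoulli distribution"; there the linearity condition is on the link scale and these weights do not carry over.

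**Conclusion.** The point holds for the continuous PSS and HSCL-25 scores. Under the written model gamma_001 is the 3-month arm difference only if that difference is linear on the chosen Time scale, and the plan neither states the spacing nor checks linearity. The weights are exact for complete data at common visit times. The biases, .02 to .10 SD for a .30 SD effect, rest on assumed trajectories and are modest against a standard error of about .10 to .14 SD. Severity is low to moderate. It is worth correcting because it touches the pilot's main estimate and the correction is cheap.

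**What to change.** In Section 9.2, Aim 2b:

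- Make visit a categorical factor (Days 0, 42, 132) with arm-by-visit terms, an unstructured within-person covariance, a family random intercept and family-clustered empirical standard errors. A more elaborate family covariance is not needed, and about two adults per family would support it poorly.
- Make the Day 132 arm contrast the key test. Report the Day 42 contrast, and the arm difference in change from Day 0 to Day 132 in place of gamma_101.
- Keep the linear model as a sensitivity analysis, stating whether Time is elapsed time or visit index.
- For binary outcomes, use the same visit factor on the link scale.

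Cost: SAP wording and a few lines of SAS, with no new data or visits. With complete data the standard error of the Day 132 contrast rises by 1/sqrt(f) - 1, which is 1.0% to 2.3% against days coding or 2.6% to 6.4% against index coding. If 10% to 30% miss Day 132 at random, the rise is about 1.3% to 4.0% or 3.3% to 10.6%. Both ranges assume a correlation between visits of .3 to .7.
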